Despite the growing evidence supporting exercise-based rehabilitation, limited research has specifically examined the added value of verbal cueing in exercise programs for breast cancer survivors, particularly those undergoing radiation therapy. This period is often associated with heightened fatigue, increased stress, and progressive musculoskeletal impairments, including shoulder stiffness and reduced ROM. Radiation therapy, while essential for cancer control, can exacerbate joint pain, muscle tightness, and systemic exhaustion, thereby contributing to elevated cortisol levels that may further impair recovery and overall health. Although multimodal exercise interventions have shown promise in improving functional outcomes and regulating stress biomarkers in various clinical populations, their specific effects particularly when delivered with structured verbal cues remain insufficiently explored in radiation-treated breast cancer survivors.

The need for targeted and comprehensive rehabilitation strategies in this population is increasingly evident due to the rising global incidence of breast cancer and the growing number of long-term survivors. A high prevalence of shoulder dysfunction, upper limb impairment, postural abnormalities, pain, lymphedema, and reduced quality of life has been documented following multimodal cancer treatments. Moreover, there is limited emphasis on structured physiotherapy programs that simultaneously address shoulder function, cancer-related fatigue, and psychological stress, as well as a lack of evidence examining the combined effects of such interventions on functional, subjective, and physiological outcomes. Exercise-based rehabilitation and targeted physiotherapy represent cost-effective and accessible approaches to restoring shoulder mobility, reducing fatigue, and improving quality of life. The use of validated and objective outcome measures, such as active shoulder ROM and salivary cortisol levels, further strengthens the clinical relevance and translational significance of such interventions.

Accordingly, the aim of the present study is to evaluate the effectiveness of a multimodal exercise program delivered with and without verbal cues on shoulder range of motion, cancer-related fatigue, and cortisol levels in breast cancer survivors undergoing radiation therapy.

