### **3. Study Protocol**

#### **3.1 Research Design Outline**

The study was conducted as a completed clinical trial among breast cancer survivors undergoing radiation therapy at Saveetha Medical College and Hospital.

Initially titled “Impact of Verbal Cueing in Multimodal Exercise Rehabilitation: A Retrospective Study in Breast Cancer Survivors Undergoing Radiation Therapy,” the trial successfully evaluated the effectiveness of a multimodal exercise rehabilitation program delivered with verbal cueing compared to the same program delivered without verbal cueing.

Participants who were undergoing radiation therapy were allocated into two groups: one group received the multimodal exercise program accompanied by structured verbal cues, while the comparison group performed the same exercise program without verbal guidance. Upon completion of the intervention period, outcomes were assessed to determine the impact of verbal cueing on physical and physiological parameters.

The outcome measures included shoulder range of motion, cancer-related fatigue, and

physiological stress levels. Shoulder range of motion was measured using a universal goniometer for shoulder flexion, abduction, and external rotation. Cancer-related fatigue was evaluated using the FACIT–Fatigue scale, and physiological stress was assessed through salivary cortisol analysis.

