**[Time Frame: Baseline and post-intervention]**

#### **4. Statistical Analysis Plan (SAP)**

The statistical analysis will be performed using IBM SPSS Statistics version 27. The study was conducted on breast cancer survivors aged 35 - 45 years undergoing or recently completing radiation therapy. The primary objective of the study was to compare the effects of two intervention protocols between Group A (MMV – Multimodal Exercise with Verbal Cues) and Group B (MMWV – Multimodal Exercise without Verbal Cues) on shoulder joint range of motion, fatigue, and salivary cortisol levels.

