##### **4.2 Secondary outcome**

The secondary outcome measures were fatigue, assessed using the Functional Assessment of Chronic Illness Therapy–Fatigue (FACT-F) scale, and salivary cortisol levels, measured in ng/mL.

A total of 36 participants were included in the study and were equally allocated into two groups, with 18 participants in Group A and 18 participants in Group B. Descriptive statistics were expressed as mean  $\pm$  standard deviation (SD). Inferential statistical analysis will include tests of normality, homogeneity of variance, paired sample t-tests for within-group comparisons, and independent sample t-tests for between-group comparisons. The level of statistical significance was set at  $p < 0.05$ .

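### Does the aim of evaluating the exercise program's effectiveness leave the plan relying on within-arm paired t-tests that cannot show it?

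*Combined protocol and SAP*

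**What the plan says.** All references are to the combined protocol and SAP.

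- **Section 2.1, aim:** "the aim of the present study is to evaluate the effectiveness of a multimodal exercise program delivered with and without verbal cues", for shoulder range of motion, fatigue and cortisol.
- **Section 2.1, evidence gap:** "limited research has specifically examined the added value of verbal cueing in exercise programs for breast cancer survivors".
- **Section 2.1, radiation period:** "This period is often associated with heightened fatigue, increased stress, and progressive musculoskeletal impairments, including shoulder stiffness and reduced ROM".
- **Section 3.1, contrast evaluated:** a "multimodal exercise rehabilitation program delivered with verbal cueing compared to the same program delivered without verbal cueing". On the comparator it says that "the comparison group performed the same exercise program without verbal guidance". No non-exercise arm is described.
- **Section 4, objective:** "The primary objective of the study was to compare the effects of two intervention protocols between Group A" (cued) and Group B (uncued). The population is described there as "undergoing or recently completing radiation therapy".
- **Section 4.2, tests:** "paired sample t-tests for within-group comparisons, and independent sample t-tests for between-group comparisons", with 18 participants per group and significance at p < 0.05. The section does not rank the two kinds of test or call either one supportive.

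**The concern.** If the section 2.1 aim is taken to mean that the exercise program itself works, the between-arm test cannot address it, because both arms receive the program. Only the paired tests would seem to speak to it, and they ask merely whether the mean change in an arm is zero.

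Zero change is a poor benchmark for no effect in these patients. By the document's own account, radiation often goes with worsening fatigue, stress and shoulder movement. Patients who have recently finished radiation might instead be recovering. A paired p-value therefore mixes the program with the background course, and the error can go either way: recovery credited to exercise, or a real benefit hidden by decline.

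Because section 4.2 lists both kinds of test under one significance threshold, an author could report a significant paired result as proof that the program works. An author could also read significance in one arm and not in the other as evidence for cueing.

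**Working it through.** The document gives no effect size, SD, power or expected background change, so there is no planned figure to reproduce. The check has two parts.

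**1. What the paired and between-arm tests respond to**

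Inputs: 18 per arm and p < 0.05 (section 4.2). Assumptions: two-sided tests, normally distributed change scores with equal SDs, and a between-arm test on change scores. Section 4.2 does not say whether change or post-intervention scores are compared.

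- Smallest significant within-arm mean change: t(0.975, 17)/√18 = 2.110/4.243 = 0.497 SD of change.
- Smallest significant between-arm difference in change: t(0.975, 34) × √(2/18) = 2.032 × 0.333 = 0.677 SD.
- Illustration with observed changes of 0.55 and 0.45 SD:
  - Within arms, t = 0.55 × 4.243 = 2.333 (p = 0.032) and t = 0.45 × 4.243 = 1.909 (p = 0.073).
  - Between arms, t = 0.10/0.333 = 0.300 on 34 df (p = 0.766).
  - The paired tests split the arms although the between-arm test sees nothing.

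Now suppose the program does nothing and patients change for other reasons. The chance that one arm's paired test shows significant improvement comes from the non-central t distribution with 17 df and non-centrality equal to the background change × √18. The background values are assumed.

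| Background change (SD of change) | Chance of significant improvement in one arm |
|---|---|
| −0.2 (worsening) | 0.3% |
| 0 | 2.5% |
| +0.2 (recovery) | 12% |
| +0.5 (recovery) | 52% |
| +0.8 (recovery) | 89% |

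In the opposite direction, a true benefit of 0.5 SD fully cancelled by worsening of 0.5 SD leaves a net change of zero. It shows significant improvement in 2.5% of trials, against 52% without the worsening.

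With the same background change in both arms and no cueing effect, simulation of the between-arm test gives rejection of about 5% at every background change tried (0 to 1.0 SD). The statistical premise is therefore sound: a paired test here does not isolate the program.

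**2. Whether the plan asks the paired tests to do that**

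- The section 2.1 aim includes the phrase about delivery with and without cues. Leaving it out is what turns the aim into exercise versus no exercise.
- The same section names the added value of cueing as the under-studied matter.
- Section 3.1 also speaks of effectiveness, and there supplies the comparator: the same program without cueing.
- Section 4 states the primary objective as a comparison of the two groups.
- Section 4.2 gives the paired tests no role beyond within-group comparison. No section says they will support a claim that the program works, or that significance will be compared across arms.

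Four of these places point to the cueing contrast, and the planned independent t-test addresses it. The fifth lists pre-post tests beside a between-group test, which is routine.

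**The case for a change.** The strongest case for acting is that the program-effectiveness reading is not contrived. Section 2.1 also says that the specific effects of multimodal exercise are under-explored in radiation-treated survivors, with cueing as a particular case. The secondary-outcomes section justifies the fatigue scale as suited to judging exercise-based rehabilitation. A reader could expect a conclusion about the program, and only the paired tests could seem to provide one. There is also a risk under the cueing reading. With shared background change of 0.5 SD and no real effect of any kind, exactly one arm shows significant improvement in about 2 × 0.516 × 0.484 = 50% of trials, which invites a claim of improvement with cues but not without. One clarifying sentence would cost almost nothing.

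Part of this stands. Section 2.1 is looser than section 4, and section 4.2 does not label the paired tests. Three things limit it:

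- The harm depends on a later author misusing a test; the plan does not prescribe that misuse.
- The large percentages need background recovery. Section 2.1 describes worsening, and sections 2.1, 3.1 and 3.3 describe patients undergoing radiation. Recovery rests on one phrase in section 4, with no proportion given. Under worsening of 0.2 SD the false-improvement rate falls to 0.3%.
- A clarification would leave every test, p-value and between-group result as it is. Section 3.1 describes the trial as completed, so the sentence could only be a reporting note.

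One reassurance should not be overstated. The 5% rate for the between-arm test assumes a similar mix of ongoing and recently finished radiation in each arm. Section 3.1 says only that participants were allocated, which does not establish that. The rate also assumes complete data. With the group-mean imputation of section 4.3 and an assumed 2 or 4 of 18 change scores imputed per arm, simulation gives between-arm rejection of about 8% or 13%. Those are separate questions, and labelling the paired tests would not touch them.

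**Conclusion.** No change to the plan follows. It is correct that an uncontrolled paired test cannot separate a program effect from the radiation course: at 18 per arm, about 0.50 SD of change is significant whatever its cause. But the aim, read whole and alongside sections 3.1 and 4, is the contrast between cued and uncued exercise, and the independent t-test answers it. Following the plan as written still meets the stated primary objective.

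What remains is a loosely worded background sentence and an unlabelled set of routine pre-post tests. A competent analyst would fill that gap by basing conclusions about cueing on the between-group comparison and treating the paired results as description. The effect on the planned analyses is nil.

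The 0.50 and 0.68 SD thresholds rest on two-sided testing, normality, equal SDs and change scores. The recovery and worsening percentages rest also on background changes that the document does not give, so they illustrate the mechanism and do not measure a defect in this trial.

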##### **4.3 Missing Data**

For breast cancer survivors who did not attend the scheduled assessment sessions, mean imputation of the corresponding outcome scores from their respective intervention group was applied to

manage missing data.

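### If assessments were missed, filling them with the own-arm mean and running ordinary t-tests on 18 v 18 lifts the post-score type I error above 5% (8.2% with two missing per arm, normal data)

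*Combined protocol and SAP*

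**What the plan says.** Section 4.3 gives the only missing-data rule: for those who did not attend a scheduled assessment, "mean imputation of the corresponding outcome scores from their respective intervention group was applied". It covers outcome scores in general, so it reaches the primary range-of-motion measures as well as fatigue and cortisol.

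Section 4.2 fixes the numbers, "with 18 participants in Group A and 18 participants in Group B", and the tests, "paired sample t-tests for within-group comparisons, and independent sample t-tests for between-group comparisons". It continues "The level of statistical significance was set at" p < 0.05, and for the summaries "Descriptive statistics were expressed as mean" with SD. There is no variance correction, multiple imputation, observed-data analysis or sensitivity analysis, and no count of missed assessments.

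The documents do not say whether the between-group test compares post scores or change scores. Section 3.1 reads more like post scores: "Upon completion of the intervention period, outcomes were assessed to determine the impact of verbal cueing on physical and physiological parameters". The line just above the SAP text names both time points: "Time Frame: Baseline and post-intervention".

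**The concern.** Filling a gap with the mean of the attenders in the same arm leaves that arm's mean where it was and makes the arm look less variable and larger than it is. A t-test run on the completed data treats the filled-in values as real observations. For post scores, the standard error and p-value then come out too small. This happens even when absence has nothing to do with outcome, so the point does not depend on any claim of biased dropout.

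The comparison affected is the one that answers the trial's question: exercise with verbal cues against exercise without. Under missingness completely at random the extra false positives fall equally in both tails (with two missing per arm, simulation puts 0.041 of the 0.082 in the upper tail), so a false difference becomes more likely in either direction. If absence is related to fatigue or stress, the errors need not be symmetric. The reported SDs shrink as well.

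**Working it through.** **Inputs.** 18 per arm, significance level 0.05 and an independent-samples t-test (section 4.2); own-arm mean imputation (section 4.3).

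**Assumptions.** Two-sided test, normal outcomes, equal variances, no true effect, data missing completely at random, and k post scores missing per arm, shown as a range because no count is given. Baseline is taken as observed, since section 3.3 (Recruitment) places it before the intervention.

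**Post scores, exact.** Let m = 18 − k be the number observed per arm and SS the pooled within-arm sum of squares, which imputation leaves unchanged.

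- Observed-only SE = √[SS/(2m − 2) × 2/m].
- SE after imputation = √[SS/34 × 2/18].
- Ratio r = √[m(m − 1)/(18 × 17)].
- The imputed test rejects when |t| > 2.032 on 34 df. This is the same as the observed-only t, on 2m − 2 df, exceeding 2.032 × r.
- The reported SD is multiplied by √[(m − 1)/17].

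With k = 0, r = 1 and the formula returns 5.0%, the stated level. With k = 2, r = √(16 × 15/306) = √0.784 = 0.886, the effective cut-off is 2.032 × 0.886 = 1.80 on 30 df, and the error is 8.2%.

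| Missing per arm | r | Effective cut-off (df) | Type I error | SE understated | SD understated |
|---|---|---|---|---|---|
| 0 | 1.000 | 2.03 (34) | 5.0% | 0% | 0% |
| 1 | 0.943 | 1.92 (32) | 6.4% | 6% | 3% |
| 2 | 0.886 | 1.80 (30) | 8.2% | 11% | 6% |
| 3 | 0.828 | 1.68 (28) | 10.3% | 17% | 9% |
| 4 | 0.771 | 1.57 (26) | 12.9% | 23% | 13% |

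With missing values in one arm only, r = √{[(2/18)/34] / [(1/m + 1/18)/(m + 16)]}. This gives 0.971 with one missing (error 5.7%) and 0.941 with two (6.5%).

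Simulation of 400,000 trials with two missing per arm gave 8.16% after imputation and 4.96% on observed values only. The Welch version of the imputed test (100,000 trials) gave 8.19%.

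**Skewed post scores (simulation, lognormal).**

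| Log-SD | Imputed, one missing | Imputed, two per arm | Observed only |
|---|---|---|---|
| 0.5 | 5.3% | 7.9% | 4.7% |
| 1.0 | 4.5% | 7.1% | 3.8% |

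**Change scores and the paired test (simulation, 400,000 trials per cell).** Baseline and post variances are equal and only post values are imputed.

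| Baseline-post correlation | Change score, 1 per arm | 2 per arm | 4 per arm | Paired, 1 missing | 2 missing | 4 missing |
|---|---|---|---|---|---|---|
| 0.5 | 5.6% | 6.4% | 8.1% | 5.6% | 6.3% | 7.9% |
| 0.8 | 5.6% | 6.1% | 7.7% | 5.4% | 5.9% | 7.3% |
| 0.9 | 5.3% | 5.8% | 7.3% | 5.0% | 5.3% | 6.6% |
| 0.95 | 4.9% | 5.3% | 6.9% | 4.6% | 4.6% | 5.7% |

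A separate run of the change-score test with two missing per arm, over correlations 0 to 0.9, gave 5.9% to 6.5%. Observed-only change and paired tests stayed between 4.9% and 5.1% in every cell.

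The reversal at high correlation has a simple cause. With unit variances, a true difference has variance 2(1 − ρ), whereas an imputed one (arm mean minus own baseline) has variance of about 1. At ρ = 0.95 with two of 18 imputed, the average variance is about (16 × 0.10 + 2 × 1)/18 = 0.20 against a true 0.10, so the SD of differences is overstated by about √2, or 41%.

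**The case against.** The strongest reply is that 8.2% is not this trial's error rate. It needs exactly two missing post scores in each arm, and the documents never say that anyone missed an assessment. The past tense in section 4.3 is weak evidence of use, because the SAP mixes past and future tense throughout. This stands: the figure is an illustration. It does not rescue the rule, which is wrong whenever it is used, and the trial is described as finished ("The study was conducted as a completed clinical trial"), so the count should be known.

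Second, the headline takes the test with the most inflation. The outcome sections describe improvement from baseline, so change scores are plausible, and the excess with two per arm is then about one percentage point rather than three. This also stands, and is why both sets of figures are given.

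Third, the result depends on the distribution. With strong skew and one missing value the error is 4.5%, below 5%, although still above the 3.8% of the observed-only test. The claim is therefore limited to roughly normal data.

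Fourth, observed-only t-tests restore 5% only if data are missing completely at random, and any re-analysis now is post hoc. Both are true and must be stated with the results. Finally, calling two per arm material is a judgement; the documents set no threshold. Two of 18 is 11% missing, and 8.2% is 1.64 times the stated level.

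**Conclusion.** The concern holds. As written, the rule combined with uncorrected t-tests understates the post-score standard error whenever a value is missing. For two-sided tests on roughly normal, equal-variance data missing completely at random, the between-group post-score error runs from 5.7% (one missing in total) to 12.9% (four per arm). The effect is nil with none missing, small with one, and in my judgement material from two per arm.

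For change scores and the within-arm paired test the error is usually above 5%, but by less. At a correlation of 0.95 it can fall below 5%. The size in this trial cannot be fixed without the number missing and the choice between post and change scores. It should be fixed because the mechanism is certain and the correction needs no new data.

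**What to change.** - Delete the arm-mean rule. Run the planned independent and paired t-tests, and the descriptive SDs, on observed values only.
- Acceptable alternatives are a baseline-adjusted ANCOVA or mixed model on observed data, or multiple imputation using arm and the participant's own baseline, pooled by Rubin's rules.
- Report the number missing by arm, visit and outcome, and state whether the between-group test uses post or change scores.
- Label the change as post hoc and show the results under the arm-mean rule beside it. If no assessment was missed, saying so is enough.

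**Cost.** One paragraph of SAP wording and a re-run. For the post-score test, the difference needed for p < 0.05 is multiplied by t(0.975, 2m − 2)/(2.032 × r). It rises by about 6%, 13%, 22% and 31% with one to four missing per arm, so some nominal significance may be lost. For the paired test, the change with two and four missing is +7% and +16% at correlation 0.5, about −1% and 0% at 0.8, and −11% and −16% at 0.9. Observed-only tests do not remove bias if absence depends on outcome.

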#### **4.4 Rights and Risks to participants**

##### **Rights**

Participants had the right to withdraw from the study at any time without providing any explanation. They were free to decline or refrain from answering any questions related to the study procedures. Participants also had the right to seek clarification and ask questions regarding the assessments or intervention procedures at any stage of the study, either before commencement or during the course of assessments and interventions. Participation in the study was entirely voluntary and did not involve any remuneration or reimbursement.

##### **Risks**

Researcher does not anticipate any risk from this research study.

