## **2. Introduction**

### **2.1 Background & Aims**

Breast cancer is one of the most prevalent malignancies affecting women worldwide, and advances in treatment modalities such as surgery, chemotherapy, and radiation therapy have substantially improved survival rates. However, despite improved prognosis, many survivors experience persistent long-term physical and psychological complications following treatment. Reduced shoulder range of motion (ROM), cancer-related fatigue (CRF), and heightened stress levels are among the most commonly reported adverse outcomes. These complications are often the result of radiation-induced fibrosis, post-surgical scarring, muscular tightness, and systemic fatigue, with elevated cortisol levels serving as a physiological indicator of chronic stress. Collectively, these impairments negatively affect functional independence, limit participation in daily activities, and reduce overall quality of life among breast cancer survivors.

Exercise has emerged as a safe, effective, and non-pharmacological strategy to address many of these treatment-related sequelae. Multimodal exercise programs incorporating aerobic training, resistance exercises, flexibility training, and mind–body components have demonstrated beneficial effects on physical function, fatigue reduction, and stress modulation in cancer populations. Nevertheless, the effectiveness of these programs may vary depending on factors such as program delivery, patient engagement, and the quality of instruction provided during exercise sessions. Verbal cueing defined as structured linguistic instructions, motivational prompts, and corrective feedback delivered during exercise—has been shown in sports science and rehabilitation literature to enhance motor learning, improve biomechanical performance, increase adherence, and optimize exercise outcomes. By directing attention, reinforcing correct movement patterns, and promoting motivation, verbal cues may play a critical role in maximizing the therapeutic benefits of exercise interventions.

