### **3.3 Administration**

**TABLE- 1(MMV protocol)**

Phase	Activities
1. Warm-Up	- Marching in place

(5 – 10 minutes)
	
 
- Arm swings and ankle pumps
 
- Neck and shoulder rolls
 

2. Aerobic exercise (15 – 20 minutes)
	
 
-Walking depending on progress and tolerance or
 
-Cycling
 

3. Resistance Training (15 – 20 minutes)
	
 
- Bodyweight (push-ups, squats, lunges)
 
- Resistance bands/light weights (bicep curls, shoulder press, leg extensions).
 
- Progression: Gradually increase reps, sets, or intensity as tolerated.
 

4. Flexibility and Stretching (5 to 10 minutes)
	
Static stretching: Shoulders, elbows, wrists, quadriceps, hamstrings, and calves.
 
Hold each stretch for 15-30 seconds.

5. Relaxation and Cool down (5 – 10 minutes)
	
 
- Deep breathing,
 
- Ankle pumps and
 
- Neck/ Shoulder rolls
 

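### The plan anticipates no risk and describes no adverse-event recording, so pain, arm swelling, injury and stopping because of them would go unreported by arm

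*Combined protocol and SAP*

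**What the plan says.** Under 4.4 Rights and Risks to participants, the Risks text is a single sentence: "Researcher does not anticipate any risk from this research study".

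Three other places bear on it:

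- **Population.** Section 2.1, on women after multimodal cancer treatment: "A high prevalence of shoulder dysfunction, upper limb impairment, postural abnormalities, pain, lymphedema, and reduced quality of life has been documented". It adds that radiation therapy "can exacerbate joint pain, muscle tightness, and systemic exhaustion".
- **Programme.** Table 1 (MMV protocol) has a resistance phase with push-ups, squats, lunges, bands or light weights and a shoulder press, under the rule "Progression: Gradually increase reps, sets, or intensity as tolerated". Section 3.1 says that "the comparison group performed the same exercise program without verbal guidance".
- **General rationale.** Section 2.1 also says: "Exercise has emerged as a safe, effective, and non-pharmacological strategy to address many of these treatment-related sequelae".

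The outcomes in sections 3.1, 3.1.1, 3.1.2, 4.1 and 4.2 are shoulder range of motion, FACIT-Fatigue and salivary cortisol, taken at baseline and post-intervention only. On absence, section 4.3 says: "For breast cancer survivors who did not attend the scheduled assessment sessions, mean imputation of the corresponding outcome scores from their respective intervention group" was used.

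**The concern.** A rule that progresses load according to tolerance allows that tolerance may fail. The plan does not say where such a failure would be written down. No supplied section defines, collects, grades or tabulates adverse events, and none measures pain or arm swelling. The SAP has no safety analysis. Because the document states that no risk is expected, whoever runs the analysis has no prompt to fill the gap.

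The arm matters as well as the total. Section 2.1 defines verbal cueing to include corrective feedback and credits it with reinforcing correct movement. The comparison group does the same loaded exercise without it. On the plan's own reasoning, the quality of movement under load could differ between arms, so injury or pain by arm bears on the trial's question. The report could describe benefit, or no difference, and say nothing about such events in either arm.

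**Working it through.** The plan gives no event rate, power or safety figure, so there is no stated number to reproduce. The check has two parts.

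**1. What the planned data would and would not show**

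- *Average worsening of shoulder motion, fatigue or cortisol in one arm:* visible. All three are measured before and after and compared between groups (section 4.2).
- *Pain, arm swelling or injury in an individual woman:* not visible. No measure or log is described.
- *Stopping exercise because of such an event, but attending the post-assessment:* her outcome scores are measured, but the reason for stopping is not recorded.
- *The same, and missing the post-assessment:* her score is replaced by her group's mean under section 4.3. If *k* of 18 women are absent and the attenders average *m*, the filled-in group mean is [(18 − *k*)·*m* + *k*·*m*]/18 = *m*. The absent women leave no trace in the mean, whatever kept them away.

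**2. What recording could show at this size**

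Input: 18 women per arm, 36 in total (section 4.2; 18 + 18 = 36).

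Upper limit for the true rate when zero events are seen in *n* women, one-sided 95%: 1 − 0.05^(1/*n*).

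- One arm: 1 − 0.05^(1/18) = 0.153, or 15.3%.
- Both arms: 1 − 0.05^(1/36) = 0.080, or 8.0%.

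The upper end of an exact two-sided 95% interval uses 0.025 in place of 0.05 and gives 18.5% and 9.7%.

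Chance of at least one woman with an event: 1 − (1 − *p*)^*n*. The rates *p* are assumptions, since the documents give none.

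| Assumed rate | In 18 | In 36 |
|---|---|---|
| 2% | 30% | 52% |
| 5% | 60% | 84% |
| 10% | 85% | 98% |
| 20% | 98% | over 99.9% |

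Power to detect a difference between arms with 18 in each, two-sided 0.05, normal approximation (rough at this size): about 27% for 5% versus 20%, and about 32% for 10% versus 30%, again with assumed rates.

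So at assumed rates of 5% to 10%, an event in a given arm is more likely than not, and the plan describes no place to record it. Recording would support a description by arm but not a formal comparison.

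**The case against.** The best defence has several parts.

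- **The sections do not directly conflict.** Section 2.1 attributes pain, lymphedema and shoulder dysfunction to cancer and its treatment, not to exercise, and it calls exercise safe. Table 1 keeps any weights light and ties progression to tolerance. The Risks sentence states an expectation, not a result. This stands. A reader might infer that the document contradicts itself, or that it names exercise injury as a known hazard; it does neither. A general statement about exercise still does not establish that no risk is expected in women undergoing radiation.
- **Some harm would be seen.** A reader might infer that harm by arm is wholly invisible. Range of motion is the primary outcome and fatigue a secondary one, so worsening on average would appear. This also stands; the gap is confined to discrete events and their consequences.
- **Imputation applies only to missed assessments.** It does not apply to every woman who stops exercising. Correct, and the point is limited to women who are also absent from the assessment.
- **Consent pages are not in the supplied text.** The table of contents places a risk heading under the consent forms, so fuller risk wording may exist there. That could soften the criticism of the Risks sentence. It would not supply event collection or a safety analysis, which belong with the outcomes and the SAP.
- **Participants may withdraw without explanation** (section 4.4, Rights). This limits the fix: reasons can be recorded only if offered.
- **The trial is described as completed, and the gain is small.** Prospective recording may be too late, and 18 per arm settles little about safety. Both stand, and both are reasons to state the limitation openly.

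**Conclusion.** The point holds in a limited form. The expectation of no risk is unsupported by the rest of the document, and the Risks section, section 2.1 and Table 1 must be reconciled. As described, the plan leaves pain, arm swelling, injury, and stopping because of them unrecorded by arm, and group-mean imputation can hide harm-related absence from the post-assessment.

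On size: with no recording, no event rate can be excluded. With complete recording and no events, rates up to 15.3% per arm and 8.0% overall would remain compatible with the data (one-sided 95%). These limits assume that all 18 or 36 women are followed and that events occur independently between them.

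The efficacy comparison is not invalidated by this, and nothing in the documents shows that harm occurred. The conclusion rests on the supplied text, which has no adverse-event section and none listed in its table of contents. It should be corrected before results are reported.

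**What to change.** **Text.** Reconcile the Risks sentence with section 2.1 and Table 1, and drop the no-risk claim unless the document can support it. No change to the exercise content is proposed here.

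**If any sessions remain.** At each session, record any adverse event (including pain and arm swelling) and any session not completed. For a missed post-assessment, record the reason where the participant volunteers it, with *not given* as an allowed entry, in keeping with the right to withdraw without explanation.

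**Reporting.** Give counts by arm and in total with exact confidence intervals, as description only. The counts by arm speak to verbal cueing. The total speaks to the programme as a whole, but since both arms exercise it cannot separate effects of exercise from those of radiation.

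**If the trial is finished**, as section 3.1 says. The later sections mix past and future tense, so the status should be confirmed. Report whatever existing records show, state that harms were not systematically collected, and make no safety or no-risk claim.

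**Cost.** A little more recording at sessions, or staff time for a short record review, and one descriptive table. The table will not settle whether the arms differ in safety.
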